9.5 Study size

The sample size considerations are based on the expected VTE incidence for COC_{LNG} of 10 VTE per 10,000 WY²⁰, which was agreed upon recently with CHMP in a comparable PASS that is conducted by ZEG. It is expected that FC Patch Low is associated with a VTE risk that is not higher than the risk associated with COC_{LNG}.

The study should be powered to test non-inferiority of FC Patch Low treatment regarding VTE risk in comparison to COC_{LNG} use. Sample size calculations for a non-inferiority test of two exponential survival curves [6;7] showed that an expected number of 150 VTE cases should be sufficient to reach this goal. These calculations are based on the following assumptions: 1) one-sided α of 0.05; 2) power (1- β) of 0.80 and 3) non-inferiority limit on hazard ratio of 1.5.

At an incidence rate of 10.0/10,000 WY a total of 150 VTE cases could be expected within 150,000 WY. The drop-out rate in similar studies has been approximately 0.7% per month. Assuming 1) a recruitment phase of 60 months, 2) a follow-up phase of 12 - 24 months, and 3) a loss to follow-up rate of about 5%, follow-up of 101,000 study participants (50,500 FC Patch Low users and 50,500 COC_{LNG} users) for up to 24 months would result in approximately 150,000 WY (see table 1).

Based on these scenarios, the study is sufficiently powered to exclude a 1.5-fold VTE risk for FC Patch Low users compared to COC_{LNG} users in the event that the true VTE risk among FC Patch Low users is not higher than among COC_{LNG} users.

However, precise power calculations based on actual incidences and drop-out rates should be done on the basis of follow-up data 1) before the end of the recruitment phase and 2) after availability of 30,000 WY of observation. If these calculations do not confirm the assumed incidence and drop-out rates the Safety Monitoring and Advisory Council will discuss the need to decrease or increase the number of study participants and/or follow-up times.

The sample size needed for the investigation of the VTE risk is also sufficient for the evaluation of secondary outcomes – except ATE. Acute myocardial infarction and stroke are very rare in a female population of reproductive age. This study is powered to exclude a 2.5-fold risk of ATE. This is sufficient to screen for safety signals and substantial effects.

To monitor the incidence rate and recalculate the study size, if necessary, the incidence rate observed in this study will be provided with each interim report.

²⁰ 'idiopathic' pulmonary embolism and deep venous thrombosis of the lower extremities

Table 1: Expected observation time²¹

Time after study start [month]	Sub-cohorts recruited during month						
	1	2	...	24	25	...	60
	Average number of women in follow-up						
1	1,677						
2	1,665	1,677					
...				
24	1,427	1,437	...	1,677			
25		1,427	...		1,677		
...			
60						...	1,677
...					
71							1,563
72							1,552
WY	3,097	3,076	...	2,635	2,617	...	1,059
Total WY (crude)	170,023						
Total WY (corrected for loss to follow-up and 'within study switchers' who do not contribute to exposure of starter and restarter)	~151,000						

9.6 Data management

9.6.1 Databases

Two different databases are used for data collection; the administrative database (ADB) and the study database (SDB).

The ADB is provided by ZEG to the national field organizations. Physician details, as well as data from the study participant, can be entered and maintained in this database.

The SDB is validated according to GXP rules. It contains all questionnaire data including baseline data and all subsequent follow-ups. ZEG regularly performs cross-check and

²¹ **Assumptions:** approx. 101,000 study participants recruited over 60 months (~ 1,683 per month); follow-up of study participants for 12 - 24 months; drop-out rate of 0.7% per month (e.g., 12 out of 1,683 recruited women will drop-out during the first month after recruitment; therefore the average number of women during the first month is 1,677 women $[(1,683+1,671) \times 0.5]$); loss to follow-up and loss to 'within study switchers': 11%

verification checks on the data and any inconsistencies or unanticipated answers are mailed to the field organizations for further clarification.

From the questionnaire data, event data is derived from the SDB. All disease diagnoses are coded using the ICD-10 (International Classification of Diseases). ZEG also uses additional codes for the coding of events that are of specific interest (e.g. VTE during pregnancy or delivery, outcome of an unintended pregnancy: induced or spontaneous abortion, delivery of a healthy child, birth defects).

Concomitant medication is coded using WHO ATC-Codes. Surgical procedures are coded using the modified operation and procedure coding list (OPS) provided by DIMDI (German Institute for Medical Documentation and Information). All other relevant information will be coded by a ZEG specific, highly standardized coding system (ZEG Coding Dictionary). All outcomes of interest are additionally described in a case narrative, the “case summary”.

9.6.2 Dataflow

When questionnaires are received from study participants, all pages are counted and the questionnaire is date-stamped. Questionnaires are to be checked for correct subject identification number, missing pages, legibility, and incomplete information on the questionnaires. Missing pages, illegible or missing information are requested from the study participants prior to data entry of the respective questionnaire.

Data is entered by double data entry via formatted entry screens designed to reflect the appearance of the questionnaire. Discrepancies between first and second data entry are identified by comparison of the two entry files within the statistical software SAS. The decision on the true entry is done by the responsible data manager at ZEG. This may require direct contact with the study participant who filled in the questionnaire. Corrections will be made to the questionnaire only after contact with the study participant or her treating physician. All corrections are dated and initialed by the data manager who received the relevant new information (e.g., via direct contact or by a copy of medical reports/documents). The incorrect entry will be crossed out; however, it must remain legible, and the correct entry will be placed next to it. The reason for any correction of medical data on the questionnaire must be documented.

Quality control of entered data will be supported by SAS plausibility programs which include range, coding, missing and date checks as well as cross-reference (consistency) checks between variables.

9.6.3 Database Freeze/Lock

For each interim analysis and for the final analysis the database is frozen at a predefined time point. The database will be ‘cleaned’ within 4 weeks of the database freeze. After the

final freeze (approximately 4 months after the last follow-up questionnaires have been sent to the study participants), no additional incoming data is entered in the database – this database will represent the final data source for all analyses. Safety copies are made of each database, so that all calculations can be repeated if necessary.

9.7 Data analysis

Based on available data and pharmacological considerations the *a priori* assumption is that use of FC Patch Low is not associated with an increased risk of VTE compared to COC_{LNG}. That is, a statistical comparison of FC Patch Low and COC_{LNG} is not expected to show a difference. Therefore, a non-inferiority design was chosen to investigate the VTE risk of FC Patch Low. The primary analysis will be based on the comparison of the upper confidence limit for the point estimate of the VTE²² hazard ratio with the predefined non-inferiority limit (see below).

The final analyses will include both an “as treated” (AT) and an intention-to-treat (ITT) analysis using Cox regression models. The safety conclusions of the study, however, will be based on the AT analyses (outcomes of interest will be assigned to the treatment she used at the time of the event) because the ITT approach (outcomes of interest are assigned to the treatment which was prescribed at study entry) potentially dilutes differences between treatments.

Incidence rates, incidence rate ratios (HRs), excess risks, as well as crude and adjusted hazard ratios will be calculated. The appropriate confounding variables will be built into the model. Based on the expectation of a small absolute number of serious outcomes of interest the number of confounding variables will be limited to well-established risk factors for these outcomes (e.g., age, BMI, duration of current use, and VTE history). The final decision on the confounding variables will be made by the Safety Monitoring and Advisory Council before the first interim analysis of follow-up data. In addition, alternative analysis will be performed with other potential baseline risks to check the appropriateness of this decision. Similar analyses will be performed for all VTE (cf. Section 8) and arterial thromboembolism (e.g., acute myocardial infarction and stroke), the other secondary variables and other serious adverse events.

The null hypothesis to be tested is: $HR_{VTE} \geq 1.5$ (i.e., the VTE hazard ratio for FC Patch Low vs. COC_{LNG} is higher than or equal to 1.5). The alternative hypothesis is: $HR_{VTE} < 1.5$.

In the case of VTE it is conceivable that the proportional hazard assumption that effect parameters multiply hazard does not hold. Therefore, time-dependent factors will be included in the Cox model. The appropriateness of the model will be checked by comparing results of this analysis with results of an alternative analysis which stratifies by time of

²² DVT of the lower extremities and pulmonary embolism, cf. Section 8

exposure. This stratification addresses also the potential problem of effect modification by current duration of use.

Real-life field studies frequently face the situation of missing data. The multiple reasons include superficial reading of the questions, misunderstanding of the questionnaire or simply unwillingness to give certain information. The questionnaires of this study have a clear layout and most questions have been tested in several former studies in large populations. The amount of missing information will be minimized by contacting participating women several times. If the missing information can also be collected by the enrolling physician (e.g. any information on prescription, details regarding pregnancies, etc.), he/she will be contacted. If these strategies are unsuccessful, missing variables will be either accepted or, for certain variables, e.g. BMI, the last value will be carried forward. In general, missing data will comprise less than 5% of all data collected based on the experience of comparable studies conducted by ZEG.

In addition to the before mentioned main analysis, an automated selection method will be used to arrive at a more parsimonious model. A backward stepwise approach will be used to reduce the number of covariates in each analysis/sub-analysis. The pre-specified significance level for removal or addition of a covariate will be $p > 0.10$ and $p < 0.05$, respectively. However, there is no general agreement in the scientific literature about the most appropriate method for covariate selection or whether it should be applied at all. The latter view is based on the general request that the selection of relevant prognostic factors should be content driven (i.e., which factors are potential confounders). Therefore, the backward stepwise approach will only be performed for exploratory purposes.

A detailed statistical analysis plan addressing descriptive and inferential statistics will be developed by the study team during the first year after study start. This plan will include methodological details (e.g., censorship at time of cancer diagnosis, surgery or occurrence of other acute VTE risk factors for the analysis of VTE), a specification of sub-analyses (such as stratification by dose of ethinylestradiol (e.g., HR_{VTE} for FC Patch Low vs. COC_{LNG} with 20mcg of ethinylestradiol) and current duration of use (e.g., HR_{VTE} during the first year of use)) as well as a comprehensive set of mock tables for the presentation of the study results. The final analysis plan will be approved by the Safety Monitoring and Advisory Council before the first interim analysis of follow-up data. Changes of this document are to be approved by the Safety Monitoring and Advisory Council.

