Multinational, controlled, prospective, active surveillance study that follows two cohorts. The cohorts consist of new users (starters³ and restarters⁴) of two different groups of hormonal contraceptives: FC Patch Low and COC_{LNG}. The study will use a non-interference⁵ approach to provide standardized, comprehensive, reliable information on these treatments in a routine clinical practice setting. Study participants will be enrolled via an international

² cf. Section 9.2.1

³ First ever user of a CHC

⁴ User who restarts hormonal contraceptive use with a CHC (same CHC as before or new CHC) after an intake break of at least two months.

⁵ I.e., 1) all new users of FC Patch Low or COC_{LNG} are eligible for enrollment if they give their informed consent; and 2) the physician's prescribing, diagnostic, or therapeutic decisions take place before study participants are recruited.

network of 2,000 – 3,000 CHC prescribing health care professionals. Study participants will be followed up for 24 months. All outcomes of interest will be captured by direct contacts between the investigator team and the study participants. Reported outcomes of interest will be validated via attending physicians and relevant source documents. The classification of outcomes of interest into ‘confirmed’ and ‘not confirmed’ will be verified by blinded independent adjudication.

Population

Approximately 101,000 study participants (50,500 FC Patch Low and 50,500 COC_{LNG} users) will be recruited via a network of 2000 – 3000 CHC-prescribing health care professionals (e.g. gynecologists and general practitioners) in approximately 6 European countries. All starters and restarters (see above) of FC Patch Low or COC_{LNG} who are willing to participate in the study are eligible for enrollment into the study⁶.

Variables

Primary statistical variable: VTE hazard ratio for FC Patch Low vs. COC_{LNG} adjusted for age, BMI, duration of current use and family history of VTE. Results are based on patient-reported VTE that will be validated via the attending physicians and medical records. Other variables include arterial thromboembolism, cancer, pregnancy related data, application site reactions and serious adverse events.

Data sources

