9.2.4 Follow-Up Phase

ZEG will perform all follow-up activities during this phase of the study. All subjects who provide written informed consent will be contacted for follow-up regardless of the duration of treatment or whether they discontinue treatment. Subjects who withdraw their consent for follow-up will not be contacted. The funder will not have access to names, addresses, or alternative contact information for the subjects.

Follow-up questionnaires will be mailed to the study participants at 6, 12 and 24¹⁸ months after study entry to collect information regarding major safety outcomes.

The specific safety data to be collected during follow-up will focus on VTE (in particular deep venous thrombosis of the lower extremities and pulmonary embolism), arterial thromboembolism (in particular AMI and stroke), the outcomes reflecting the other secondary objectives as well as all other serious adverse events,¹⁹ including cancer and specifically gynecological cancers. Subjects who report any of these outcomes will be asked to provide their primary care physician's/treating physician's name and address information. ZEG will contact the relevant physician (the attending physician is in most cases not the recruiting physician) and inform him/her about the study objectives and will share the subject's informed consent to access her medical information. Follow up by ZEG will include obtaining hospital records and/or discharge summaries, medical history, treatment dates, and concomitant medication use. A qualified medical expert (i.e., pharmacovigilance physician) on the ZEG study team will assess the likelihood of a causal relationship to study treatment for each serious or unexpected adverse drug reaction in accordance with a predefined algorithm (cf. Section 9.10.3).

At each follow-up contact, subjects will be asked about the exact details and timing of their oral contraceptive use, and whether they continue to use the prescribed study medication.

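### Accepting missing covariates or carrying the last value forward is a weak rule for the baseline confounders of the adjusted primary hazard ratio; the likely loss is modest and multiple imputation would avoid most of it

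*Protocol*

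**What the plan says.** The Abstract (Variables) defines the primary statistical variable as the VTE hazard ratio for FC Patch Low against levonorgestrel-containing COCs, "adjusted for age, BMI, duration of current use and family history of VTE". Section 9.2.3 lists age, BMI and personal and family history among the items recorded at the baseline visit. Section 9.7 gives a slightly different example list of confounders and leaves the final choice to the Safety Monitoring and Advisory Council.

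On missing values, section 9.7 relies first on prevention: "The amount of missing information will be minimized by contacting participating women several times", with the enrolling physician as a second source where possible. If that fails, "missing variables will be either accepted or, for certain variables, e.g. BMI, the last value will be carried forward". It then offers the reassurance that "missing data will comprise less than 5% of all data collected based on the experience of comparable studies".

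The study size (section 9.5) rests on "1) one-sided α of 0.05; 2) power (1- β) of 0.80 and 3) non-inferiority limit on hazard ratio of 1.5", which gives 150 expected VTE cases. The 11% correction in Table 1 covers loss to follow-up and within-study switching only. The planned re-check of power concerns incidence and drop-out rates.

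**The concern.** Many protocols leave missing covariates to the analysis plan. This one states a method with two options, and an analysis plan that follows it inherits them. Neither suits a baseline confounder in the primary model.

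- **Carry-forward** needs an earlier value. If BMI or family history is missing at the baseline visit, there is none.
- **Acceptance** leaves a blank in the covariate set. Standard Cox software excludes a record with a blank covariate, so the default consequence is a complete-case analysis. This is an inference from how such models are fitted; the protocol does not state it.

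The 5% forecast does not settle the matter. It refers to all data items together, and gaps may concentrate in a few questions; section 9.7 itself names unwillingness to give certain information as a cause. Two things are at stake: events lost from a design planned at almost exactly 80% power, and possible bias in the hazard ratio on which the non-inferiority decision rests.

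**Working it through.** **Inputs.** From section 9.5: one-sided alpha 0.05, power 0.80, margin 1.5, 150 expected events, and a true hazard ratio of 1.0 (the study is powered "in the event that the true VTE risk among FC Patch Low users is not higher than among COC_{LNG} users"). From section 9.2.2: 1:1 recruitment. The share f of VTE cases lost through incomplete covariates is not given, so it is an assumption. The 5% used below applies the protocol's item-level ceiling to cases, for scale only.

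**Reproducing the plan's figure.** Events = 4(1.645 + 0.842)² / (ln 1.5)² = 150.4, which agrees with the stated 150.

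**Power with D events.** Power = Φ(½√D × ln 1.5 − 1.645). With D = 150 this is 79.9%. Table 1 gives 170,023 × 0.89 ≈ 151,300 woman-years, or about 151 events, and 80.1%.

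**Power after losing a share f of the 150 events:**

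| f | Events left | Power |
|---|---|---|
| 0 | 150.0 | 79.9% |
| 1% | 148.5 | 79.6% |
| 2% | 147.0 | 79.2% |
| 5% | 142.5 | 78.1% |
| 10% (assumed) | 135.0 | 76.1% |

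The 10% row is close to 5% missing independently on each of two covariates: 1 − 0.95² = 9.75%, leaving 135.4 events and 76.2%. Offsetting a 5% loss by size alone would take 150.4/0.95 ≈ 158 events, or 101,000/0.95 ≈ 106,300 women.

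**Bias.** Take a true hazard ratio of 1.0 and compare rates within levels of the confounder. Complete-case analysis multiplies the ratio by

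(share of patch cases kept / share of comparator cases kept) ÷ (share of patch person-time kept / share of comparator person-time kept).

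- Loss depends only on cohort and confounder: cases and person-time in each cell lose the same share, so the factor is 1.00.
- Loss depends on outcome equally in both cohorts (1% of cases, 5% of person-time): (0.99/0.99) ÷ (0.95/0.95) = 1.00.
- 5% of patch cases lost against 1% of comparator cases, person-time loss equal: 0.95/0.99 = 0.96. With the cohorts reversed: 0.99/0.95 = 1.04.
- 10% against 0%: 0.90. Reversed: 1/0.90 = 1.11.

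Bias therefore needs a loss of cases relative to non-cases that differs between cohorts. These percentages are illustrations; the protocol gives none.

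**The case against.** The strongest reply is that an accepted gap need not remove the woman. A missing category, or another rule in the analysis plan, would also fit the text, and section 9.7 defers methodological detail to that plan. This stands as a reason for calling the exclusion an inference. It does not rescue the stated options: neither recovers a missing baseline value, and the protocol names no alternative.

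Second, the protocol works hard to prevent gaps. Physicians check the women's answers (9.4), missing items are clarified by telephone (9.4) and requested before data entry (9.6.2). In addition, exposure is validated through prescribers (9.10.1). Age and duration of current use are therefore unlikely to be missing often. This stands and keeps the expected effect small.

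Third, power may have a little slack. Rebuilding Table 1 from its stated recruitment and drop-out assumptions gives about 157,000 to 158,300 woman-years after the 11% correction, hence 81.5% to 81.7% power, and 79.7% to 80.0% after a 5% loss. The Council may also enlarge the study after the planned re-check. Both points soften the concern, although the re-check is not aimed at missing covariates.

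Fourth, carrying BMI forward over at most 24 months is a minor source of error. That is right for later updates of a recorded value, and no objection is made to it.

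**Conclusion.** The point holds as a modest, inexpensive improvement. The stated rule cannot fill a missing baseline confounder. It probably leads to a complete-case primary model, and the item-level forecast of under 5% does not limit how many women or cases that would exclude. The cost is about 2 percentage points of power if 5% of events are lost, and about 4 if an assumed 10% are lost. Both figures assume 150 planned events, a true hazard ratio of 1.0, and exclusion of women with an accepted gap.

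A reader might infer more, and the documents do not support it:

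- **Power of 72% to 74%.** This needs 5% independent missingness on three or four covariates (for four, 1 − 0.95⁴ = 18.5%, 122 events, 72.4%), which must include age or duration of current use. Nothing in the protocol suggests that.
- **Inflated incidence.** Crude rates are events over woman-years and need no covariates; nothing restricts them to women with complete data.
- **A hazard ratio biased because case records are better completed.** For reported outcomes, "Follow up by ZEG will include obtaining hospital records and/or discharge summaries, medical history, treatment dates" may indeed fill gaps for cases. If this happens equally in both cohorts, the ratio is unchanged, and fewer events are lost. No passage indicates a difference between cohorts, and section 9.2.5 blinds case assessment to the study drug. Bias is possible in either direction but not shown.

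**What to change.** In section 9.7, for baseline covariates of the primary model, replace acceptance or carry-forward with multiple imputation. The imputation model should include cohort, the event indicator, the cumulative baseline hazard and all covariates of the analysis model. Base the adjusted primary hazard ratio on the imputed data and report complete-case analysis as a sensitivity analysis. Carry-forward may stay for later updates of values such as BMI, but not for values missing at baseline.

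The cost is a change of wording, some programming on about 101,000 records, and a missing-at-random assumption that must be stated. No change to recruitment or data collection is needed. Since all women stay in the model, the event count stays at about the planned 150 and power close to 79.9%.
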